#### **OBJECTIVE**

The objective is to evaluate the efficacy of two topical picaridin-based repellents against mosquitoes in two field locations. The sponsor believes the two repellent products will produce an effective mosquito repellent for up to 12 hours. Therefore ICR will conduct field studies to assess repellency of these test samples.

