#### Number of subjects and Rationale for Sample Size

The EPA Guideline (EPA/OPPTS Guideline \$10.3700) recommends at least six test subjects be used. Because of the cost of doing field studies, it is prudent to ensure data collected will give a good representation of the repellency of the test formulations. In a published paper the number of subjects required to achieve an estimated among-subjects standard deviation for specific times of 0.5 hours to 2.0 hours was calculated for protection times from 1 hour to 8 hours. The number of subjects required to achieve an estimated among-subjects standard deviation of 2.0 hours at a 95% confidence level for an 8 hour protection time was calculated to be between 10 and 11 subjects. This study, therefore, will use ten treated test subjects. There will be an additional two control subjects, plus two additional treated test subjects to replace anyone that either drops out or is ineligible to participate due to a positive pregnancy test or other unforseen circumstances. These additional two treated test subjects will help to ensure a minimum "n" of ten and will aid in protecting the privacy of any dropouts.

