#### **METHODS**

#### Experimental Design

This is a subject-blinded study. The delineated areas on the arms of subjects will be treated and used as test areas. Only arms are being treated in this study, in an attempt to further reduce the areas available for mosquitoes to bite. In addition, arms are quite easy to monitor for mosquito activity. Therefore there will be twelve test arms for each treatment. Each test subject will have one arm treated with one of the two test products and the other arm will be treated with the other test product.

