#### DATA ANALYSIS:

Efficacy data will be reported as Protection Time which is the mean hours and minutes to FCB or test termination. We will calculate the time of complete protection for the test repellents. Therefore, the time to first confirmed bite for all treated test subjects will be averaged and the standard deviation computed. A 95% confidence limit will be determined. If a test subject protection time appears to be an "outlier" (one that appears to deviate markedly from the other members of the sample in which it occurs), that data will be subjected to the test for outlying observations as described in ASTM E 178-94 "Standard Practice for Dealing With Outlying Observations". If the test indicates that the observation is an outlier, that data point

If a test subject wishes to drop out of the study before the stated end point, the data from that test subject will not be used in calculating the mean PT of the test repellent. Any treated arms that do not breakdown within the twelve hour time frame of the study will be given a value of twelve for PT. All data will be entered into a CoStat program for the calculation of the standard deviation and the 95% confidence limit.

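### The outlier test is applied to protection times capped at 12 h, where it cannot tell a genuine early failure from an aberrant reading

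*Protocol*

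**What the plan says.** All of the rule stands in the protocol's Data Analysis section.

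- **Endpoint.** "Efficacy data will be reported as Protection Time which is the mean hours and minutes to FCB or test termination". The times are averaged, and a standard deviation and a 95% confidence limit are computed.
- **Cap.** An arm that does not break down within the study "will be given a value of twelve for PT".
- **Trigger.** A protection time is a candidate outlier if it is "one that appears to deviate markedly from the other members of the sample in which it occurs". No numeric threshold is given.
- **Test.** For such a value, "that data will be subjected to the test for outlying observations as described in ASTM E 178-94". The readable text names neither the specific test nor a significance level. It does not exempt capped samples and does not confine the test to recording or application errors.
- **Consequence.** "If the test indicates that the observation is an outlier, that data point": the sentence breaks off there in this copy, so the fate of a flagged value cannot be read.

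On the size of the sample, Experimental Design says "Therefore there will be twelve test arms for each treatment", and the sample-size section says "This study, therefore, will use ten treated test subjects", with two more treated subjects as replacements. The Objective section says "The sponsor believes the two repellent products will produce an effective mosquito repellent for up to 12 hours", so a sample with most arms at the cap is an outcome the plan anticipates.

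**The concern.** Outlier tests of this kind compare the extreme value with the sample's own mean and SD, and take the rest of the sample to be roughly normal. Here the rest of the sample may be a block of identical values at exactly 12.0 h, put there by a scoring rule. Any arm that fails then stands out because the others have no spread, and not because its reading is suspect.

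The endpoint is time to first confirmed bite. It needs a second, confirming bite, and study staff verify each bite (Criteria for Test End Point; On-Site Data Collection). A short protection time is therefore normally a real loss of protection, which is what the trial sets out to measure. If a statistical flag could take such a value out of the mean, the reported protection time would be too long and its interval too narrow. The decision to test a value is also made by eye, and under Blinding of the Study the Study Director and staff know which product is which.

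**Working it through.** The documents give no figure for the outlier test, so there is nothing of the plan's own to reproduce.

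**Inputs.** From the protocol: cap 12 h; 12 arms per product per site, with a minimum of 10; SD 2.0 h and an 8 h protection time as the planning case in the sample-size section. Assumed: a one-sided Grubbs test, with levels from 5% to 0.1%, because the readable text names neither test nor level.

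**Step 1: one arm fails at time t, the other n-1 are at 12.** Let d = 12 - t.

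- Mean = 12 - d/n, so mean - minimum = d(n-1)/n.
- Variance = [d²(n-1)/n]/(n-1) = d²/n, so SD = d/sqrt(n).
- G = (mean - minimum)/SD = (n-1)/sqrt(n). The failure time cancels.

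Critical value = [(n-1)/sqrt(n)] × sqrt(q²/(n-2+q²)), where q is the t quantile at 1 - alpha/n on n-2 df.

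| n | G, any t below 12 | 5% | 1% | 0.1% |
|---|---|---|---|---|
| 12 | 11/sqrt(12) = 3.175 | 2.285 | 2.549 | 2.791 |
| 10 | 9/sqrt(10) = 2.846 | 2.176 | 2.410 | 2.606 |

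Direct computation at t = 0.5, 4 and 11.5 h gives the same G each time. Because the square-root factor in the critical value is below 1, G exceeds it at every level. The choice of test does not matter either: a Dixon-type ratio of gap to range is (12-t)/(12-t) = 1, also its maximum.

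**Step 2: k arms fail at the same time.** G = sqrt[(n-k)(n-1)/(nk)].

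- n=12: 2.141 for k=2, 1.658 for k=3, 1.354 for k=4, all below 2.285.
- n=10: 1.897 for k=2, below 2.176.

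Tied failures are therefore not flagged at 5% at these sample sizes. (If both sites were pooled, n=24, two tied failures would give 3.247 against 2.644.) Over all 276 pairs of half-hour failure times, ties included, the earlier arm is flagged in 234 for n=12 and 202 for n=10.

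**Step 3: how often the lowest value is flagged.** Simulated samples of n=12 from a normal distribution with SD 2 h, capped at 12 h, lowest value always tested, one-sided:

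| Mean before capping | 8 h | 9 h | 10 h | 11 h | 12 h | 13 h |
|---|---|---|---|---|---|---|
| Flagged at 5% | 5% | 6% | 10% | 20.5% | 42% | 69% |

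At the 1% level, the last two are 23% and about 50.5%.

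**Step 4: effect if a flagged value were removed.** Eleven arms at 12.0 and one at 4.0:

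- Kept: mean = (11×12 + 4)/12 = 11.33 h; SD = 8/sqrt(12) = 2.31; 95% CI = 11.33 ± 2.201×2.31/sqrt(12) = 9.87 to 12.80 h.
- Removed: mean 12.00 h, SD 0, an interval of zero width.

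**The case against.** **The harm cannot be read in the document.** A reader might infer that the protocol deletes early failures. It does not show this. The sentence on flagged values is lost in extraction; the missing words could exclude the value, report it separately or keep it with a note. This objection stands, and the shift from 11.33 to 12.00 h is conditional on removal.

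**A judgement comes before the test.** A reader might infer that a lone failing arm is always flagged. The rule tests only a value that appears markedly deviant, and a failure at 11.5 h among values of 12.0 might never be submitted. The simulated rates are therefore upper bounds. This stands, although a gate with no threshold is no safeguard.

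**The exact result covers one configuration.** It needs exactly one failure with all other arms at 12.0. Under a normal distribution with mean 12 and SD 2 that has probability 12 × 0.5^12 = 0.3%; with mean 13 it is 12 × 0.3085 × 0.6915^11 = 6.4%. Most simulated flags come from other patterns, and tied failures are not flagged at n=10 or 12. This limits the algebra. The simulation covers the other patterns.

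**High outliers are possible.** It is tempting to say that the cap rules them out. It does not when few arms reach 12: values of 5, 5.5, 5.5, 6, 6, 6, 6, 6.5, 6.5, 7, 7 and 12 give a high-side G of 2.998. Only when most arms sit at the cap is the rule confined to early failures.

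**At the plan's own planning case the rate is nominal.** With mean 8 h and SD 2 h it is about 5%. That is correct, but the Objective section looks to protection up to 12 h, and the rate rises steeply towards that value.

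**Conclusion.** The concern holds in a limited form. The protocol prescribes an outlier test on data for which it is not valid, in the outcome the sponsor expects. When one arm fails, the rest are at 12 h and that arm is tested, the statistic is at its maximum whatever the failure time (3.175 for n=12, 2.846 for n=10). The test then carries no information on whether the reading is aberrant. This part is exact and does not depend on the unnamed test or level.

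More generally, the chance of flagging the lowest value runs from about 5% at a mean of 8 h to 69% at 13 h. Those figures assume normal times before capping, SD 2 h, n=12, a one-sided 5% Grubbs test and the lowest value always tested; means other than 8 h are not planning figures from the protocol. Upward bias in the mean and a falsely narrow interval follow only if flagged values are removed, which this copy neither states nor excludes.

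**What to change.** In the Data Analysis section, state that:

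- every treated arm's observed protection time stays in the primary analysis, whatever the outlier test shows;
- a value may be excluded only for a procedural failure (for example, a misapplied sample) documented before results are tabulated;
- any analysis omitting a statistically flagged value is shown only as a sensitivity analysis.

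The cost is about one sentence of protocol text and a reported mean that may be slightly less favourable. If the lost text already keeps flagged values, the change does no harm.

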The P.I. will contact all interested subjects by phone several days after receipt of the ICD to fully explain the ICD with them. All contacted people that show interest will be offered the opportunity to come to ICR to go through the consent process in person. If interested subjects are unable to travel to ICR, the consent process will be conducted on the phone. Sufficient time will be spent with each interested subject to answer any questions they may have. When both the P.I. and the interested subject are satisfied that they have meet the study qualifications for inclusion into the study, understand and are comfortable with the ICD, they will then be invited to sign the ICD. Each subject will be asked to sign and date the ICD in the presence of a witness. Their signature will acknowledge that they have been informed and freely give their consent to participate in the study. The witness will then sign and date the ICD. Each test subject giving their consent by phone will be asked to mail the signed ICD back to ICR. A copy of the signed ICD will be provided to each study subject, either by mail or in person depending upon whether consent was in person or by phone.

When a subject is available, and qualifies for a particular study, and is willing to participate based on study requirements as explained, and has signed an ICD, they will be notified of study specific travel arrangements in a follow up call closer to the study date.

ICR has been fully compliant with 40 CFR 26.1125 in obtaining written approval for all repellent studies from an independent Institutional Review Board

In the event that an interested subject declines to sign an informed consent document, they will not be permitted to participate in the study.

There is no coercion for any subject to participate. The inclusion/exclusion criteria are clear, the payment is clear, the subjects are informed of the conditions they will likely encounter and what is

Page 18 of 31

Protocol No.: G0590307001A044 ICR Project No.: 0307-059-0155

expected of them. Each consenting test subject will be informed that they may drop out of the study at any time. Further, they may leave as soon as practical after early withdrawal from the test.

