### Criteria for Test End Point

Efficacy will be evaluated by intermittent exposure of the test subjects' arms. The treated test subjects will expose their treated arms to mosquitoes for 5 minutes at approximately 30 minute intervals. At the end of each 5 minute exposure period, the treated and control subjects will be escorted back to screened enclosures where they will be seated until the next 5 minute exposure period. The test subjects will expose treated arms until the FCB (when two bites occur on the same arm in the same exposure period, or one bite occurs in each of two consecutive exposure periods, the first bite being the confirmed bite) or until 12 hours have elapsed, whichever occurs first. For the purposes of this test, a bite is defined as a mosquito penetrating the skin with its proboscis and taking sufficient blood to cause its abdomen to swell. When the two bites have occurred as noted above, the test will terminate on that arm.

When the testing is terminated for an arm, test subjects will then roll down their sleeves to cover such discontinued arms. The test will be terminated on a treated arm when a bite is followed by one additional bite (the initial bite and one confirming bite). Each bite must occur within one 5 minute exposure period or one bite must occur in each of two consecutive exposure periods. If the bites do not occur within the specified time, the number of bites required will begin anew.

Once a confirmed bite occurs, the test subjects will stop exposing that arm to mosquitoes. They will then be able to remove the bandages and tape, scratch and wash that arm. If they want to, they can use rubbing alcohol to help stop the itching from the bites they may have received. Caladryl® or Calamine® lotion may also be used.

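### The dropout rule removes both arms of a withdrawing subject, so a completed protection time on one arm is lost if its owner leaves while the other arm is still running

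*Protocol*

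**What the plan says.** The rule is in the protocol's Data Analysis section. Its trigger is: "If a test subject wishes to drop out of the study before the stated end point". Its consequence is that "the data from that test subject will not be used in calculating the mean PT of the test repellent". No exception is made for an arm that has already failed.

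Three other statements bear on it:

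- Experimental Design: "Each test subject will have one arm treated with one of the two test products", and the other arm gets the other product. Treatment Application fixes A on the right arm and B on the left.
- Criteria for Test End Point: "When the two bites have occurred as noted above, the test will terminate on that arm". The other arm goes on until its own FCB or 12 h.
- Test Subject Recruitment: subjects are told that "they may drop out of the study at any time".

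The same Data Analysis section says that "the time to first confirmed bite for all treated test subjects will be averaged and the standard deviation computed", and that an arm without breakdown by 12 h "will be given a value of twelve for PT". The averaging sentence covers all treated subjects and the 12-hour rule works by arm. The dropout rule works by subject and removes some of them.

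**The concern.** The unit of exclusion does not match the unit of observation. Suppose arm A reaches FCB at 3 h and the subject then goes home with arm B unbitten. The PT for A is fully observed, and B has about three protected hours on record. The rule as worded discards both because of something that happened after A's result was known.

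Two things are at stake. Valid outcome data are lost from a sample of 10 to 12 arms per product per site. Also, if a short PT on one arm makes a subject likelier to leave, short PTs are removed selectively and the mean rises. The Benefits section says the result is to give users a reliable estimate of protection time and to support label claims, so overstatement is the direction that matters most.

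**Working it through.** **1. Who is affected.** Taking the two-arm design and the arm-level end point together:

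| State at departure | Dropout under the rule? | What is lost |
|---|---|---|
| Both arms at FCB | No, the end point is met | Nothing |
| One arm at FCB, other running | Yes | One complete PT and one partial time |
| Neither arm at FCB | Yes | Two partial times |

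The defect that can be repaired without new methods is in the second row.

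**2. Effect of deletion on a mean.** Let *k* of 12 arms be deleted, with mean *D*, and let the rest have mean *R*. The full mean is [(12 − k)R + kD]/12, so

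change = R − full mean = (k/12)(R − D).

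- k = 1, D = 6 h, R = 10 h: (1/12)(4) = +0.33 h.
- k = 2, D = 4 h, R = 10 h: (2/12)(6) = +1.0 h (full mean (100 + 8)/12 = 9.0 h, against 10.0 h).
- k = 1, with an unbitten leaver whose arm would have lasted 12 h, and R = 9 h: (1/12)(9 − 12) = −0.25 h.

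The sign therefore depends on who leaves. All values of D and R are assumed.

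**3. Average bias under a two-arm model.** The protocol gives 12 treated subjects per site, two arms each and a 12 h cap. It gives no dropout rate and no PT distribution, so the following are assumptions: PT normal with mean 9 h and SD 3 h, capped at 12 h; within-subject correlation between arms 0, 0.3 or 0.6; a subject whose first arm fails before 6 h leaves with chance p. Bias is the mean after the rule minus the mean of all arms. I ran 100,000 simulated sites per setting; the full mean is about 8.75 h.

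| p | Dropouts per 12 | Bias, protocol rule | Bias if the completed arm is kept and only the unfinished arm left out |
|---|---|---|---|
| 0.1 | 0.3 to 0.4 | +0.06 to +0.08 h | −0.01 to +0.02 h |
| 0.2 | 0.6 to 0.7 | +0.12 to +0.16 h | −0.01 to +0.04 h |
| 0.3 | 0.9 to 1.1 | +0.19 to +0.24 h | −0.02 to +0.06 h |

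Ranges are over the three correlations. With the same number of withdrawals at random, the bias is 0.00 h.

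**4. Sensitivity to the withdrawal model.** These runs assumed mean PT 8 to 11 h and SD 2.0 or 3.3 h.

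- Subjects whose first arm fails before 8 h leave with chance 0.25 to 0.5: +0.06 to +0.68 h, with 0.3 to 4.5 dropouts per 12.
- Subjects are equally likely to leave after a first failure whenever it occurs: about 0.00 to +0.26 h.

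**The case against.** **The rule can be read by product.** It speaks of the mean PT of the test repellent in the singular, and the end point it refers to is reached arm by arm. On that reading a failed arm has met its end point and stays in. This is possible, but the text excludes the data from that subject and says nothing about keeping a completed arm. The ambiguity is itself a reason to rewrite the sentence.

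**Bite-driven withdrawal is assumed.** This stands. The protocol gives neither a dropout rate nor reasons. Several features work against leaving: people sensitive to mosquito bites are excluded, two bites end an arm, a finished arm is covered and may be washed and soothed, the exposure is a single test day, and pay is hourly with overtime.

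**The effect is small in the moderate case.** This also stands. The range +0.06 to +0.24 h is about 4 to 14 minutes, less than half of one 30-minute exposure interval.

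**Two spare treated subjects are provided.** They protect the minimum of ten per product. They do not protect against selective loss.

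**A stronger inference.** A reader might conclude that the rule inflates mean PT by an hour or more. The +1.0 h example needs two of 12 subjects, each with exactly one arm failed at 4 h, to leave while the other arm is running. It is a constructed extreme. Nor do the documents support saying that the bias is always upward: an unbitten subject who leaves late takes a long PT out of the mean.

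**Conclusion.** The concern holds in a limited form. As worded, the protocol discards an observed, complete PT when its owner leaves with the other arm unfinished, although nothing in the design requires this. The loss of valid data does not depend on why the subject left.

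Bias is conditional. It is upward if early failures are likelier to leave: about +0.06 to +0.24 h for assumed withdrawal chances of 10 to 30% among subjects whose first arm fails before 6 h, and larger under stronger assumptions. It is zero if withdrawal is unrelated to bites, and possibly downward if long-protected, unbitten subjects leave. These figures rest on an assumed PT distribution, and the true size cannot be derived from the protocol. In the model, keeping the completed arm brings the bias to between −0.02 and +0.06 h. The change is worth making because the rule gives a worse answer than a simple alternative, not because a large distortion has been shown.

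**What to change.** Replace the dropout sentence in Data Analysis with: *An arm that reached FCB before withdrawal keeps its PT in the analysis of that product; only an arm without FCB is incomplete.*

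For the incomplete arm:

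- Preferably, treat it as right-censored at the subject's last completed exposure in a time-to-event summary (Kaplan-Meier). Add that time to the treatment data sheet, which as reproduced shows bite times by arm but no field for it.
- If the arithmetic mean is kept, leave out the incomplete arm alone. A censored time cannot be entered into that mean as if it were a PT.

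Report the number of withdrawals, the reasons, and the bite status of each arm at departure. Include any unconfirmed single bite, because an arm bitten once whose owner leaves before confirmation counts as incomplete, so some selection can remain.

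Keeping completed arms costs one sentence and no new method, since staff already record each bite time. Censoring adds one recorded time and a small amount of analysis.

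### Arms still unbitten at 12 h are averaged as if they failed at 12 h, giving an unlabelled mean restricted to 12 h whose SD and 95% interval are unreliable when many arms last that long

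*Protocol*

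**What the plan says.** The Study Rationale defines PT as the interval from application to the FCB. Criteria for Test End Point has each arm exposed until FCB "or until 12 hours have elapsed, whichever occurs first".

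The Data Analysis section then fixes the summary: "Efficacy data will be reported as Protection Time which is the mean hours and minutes to FCB or test termination". Arms with no FCB are handled by an explicit rule: "Any treated arms that do not breakdown within the twelve hour time frame of the study will be given a value of twelve" for PT. From those values, "the time to first confirmed bite for all treated test subjects will be averaged and the standard deviation computed", and "A 95% confidence limit will be determined". The section names no method for censored data and does not describe the result as a restricted mean. Subjects who drop out are left out of the mean.

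The Objective states the sponsor's belief that the products "will produce an effective mosquito repellent for up to 12 hours", so the cap lies at the top of the duration the sponsor hopes to show.

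**The concern.** An arm unbitten at 12 h has no observed PT under the protocol's own definition. Entering 12.0 as an observed failure time pulls the mean below the true mean PT. It also piles values up at one point, so the SD comes out smaller than the true spread among subjects, and the interval built from that SD is too narrow.

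This mean and its interval are the study's efficacy result, which the Benefits section says should give users a reliable estimate of protection time. If many arms last the full 12 h, the outcome the sponsor hopes for, the interval is least trustworthy. In the extreme case it expresses complete certainty from 10 to 12 people. The rule is written into the protocol, so it is not a detail left open for a later analysis plan.

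**Working it through.** **Inputs.** Cap c = 12 h (Criteria for Test End Point; Data Analysis). Arms per product and site: n = 12 planned, minimum 10 (Experimental Design; Number of Subjects). The SD at 12 h is not given. I take 2 h, the figure quoted in the sample-size section for an 8 h PT, and also try 1 h and 3 h. Assumptions: normal PT, all arms followed to 12 h, two-sided t interval (the protocol gives neither the formula nor the sidedness). The protocol states no expected mean or interval under this rule, so there is no planned figure to reproduce.

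**Step 1: what the planned mean estimates.** With a = (c − μ)/σ, the expected value of the capped time is

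E[min(T, c)] = μΦ(a) − σφ(a) + c[1 − Φ(a)].

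- μ = 12, σ = 2: a = 0, so 12(0.5) − 2(0.3989) + 12(0.5) = 11.20 h.
- μ = 13, σ = 2: a = −0.5, so 13(0.3085) − 2(0.3521) + 12(0.6915) = 11.60 h.

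**Step 2: behaviour of the planned interval.** Simulation: draw n values from N(μ, 2), cap at 12, compute the t interval. Results for n = 12:

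| True mean (h) | Arms capped | Reported mean (h) | Average SD (h) | Covers true unrestricted mean | Covers mean restricted to 12 h |
|---|---|---|---|---|---|
| 8 | 2% | 7.98 | 1.92 | 95% | 95% |
| 10 | 16% | 9.83 | 1.70 | 95% | 94% |
| 11 | 31% | 10.60 | 1.45 | 92% | 93% |
| 12 | 50% | 11.20 | 1.11 | 36% | 90% |
| 13 | 69% | 11.60 | 0.74 | 0% | 84% |
| 14 | 84% | 11.83 | 0.41 | 0% | 72% |

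At n = 10 and a true mean of 12 h, coverage of the unrestricted mean is 54%. With SD 1 h or 3 h and a true mean of 12 h, the reported mean is 11.60 h or 10.80 h, and coverage is again about 36% (n = 12) or 53% to 55% (n = 10).

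**Step 3: direction of the misses.** Against the unrestricted mean at 12 h or more, every miss has the upper limit below the truth. The lower limit cannot exceed 12 h, so it cannot miss on the other side. Against the restricted mean, most misses go the other way: the lower limit is too high in about 9% of trials at a true mean of 12 h and about 15% at 13 h (n = 12), against a nominal 2.5%.

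**Step 4: cases that need no distribution.**

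- *Every arm lasts.* All values are 12.0, so SD = 0 and the interval is 12.0 to 12.0. The exact two-sided 95% lower bound for the proportion protected at 12 h is 0.025^(1/n): 0.025^(1/10) = 0.69 and 0.025^(1/12) = 0.74.
- *Illustrative mixed result.* FCB at 9, 10, 10.5, 11 and 11.5 h, with seven arms unbitten at 12 h. The mean is (52 + 84)/12 = 11.33 h and the SD is 1.01 h. The half-width is 2.201 × 1.0075/√12 = 0.64, so the interval is 10.69 to 11.97 h. It excludes 12 h although 7 of 12 arms lasted to 12 h. A censored-normal fit to the same data gives a mean of 12.31 h and SD 1.95 h. The exact 95% interval for 7/12 protected is 28% to 85%.

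**The case against.** **The target is the restricted mean.** The protocol says it reports the "mean hours and minutes to FCB or test termination", which with full follow-up is in substance the mean restricted to 12 h. Judged against that target, coverage is 90%, 84% and 72%, not 36% and 0%. This stands, and the low figures must not be quoted without naming their target. It does not clear the plan: the quantity is not labelled, the PT definition points to the unrestricted time, and the interval still under-covers when censoring is heavy.

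**The error is conservative.** The mean is biased downward, and at true means of 12 h or more the interval misses the unrestricted mean only by understating protection. A reader might infer from 0% coverage that the product would be over-claimed. The documents and the calculation do not support that. What remains on the other side is overstated precision: an SD that is too small, a zero-width interval when all arms last, and a lower limit that is too often too high for the restricted mean.

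**Heavy censoring may not occur.** The Objective's 12 h is an upper figure, the Study Rationale cites earlier experience of 8 h and beyond, and the sample-size section works with 8 h. At true means of 8 to 10 h with SD 2 h the rule does almost no harm. A reader might take heavy censoring as the expected case. The protocol shows only that the sponsor hopes for durations at which it would arise.

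**Early termination.** A reader might see a contradiction between averaging to test termination and assigning twelve to every unbroken arm, and conclude that a cancelled test would be credited with unobserved hours. The text does not establish this. The Study Overview and Criteria for Test End Point let termination mean breakdown or the 12 h end, and weather or low-activity stops are called cancellation. The wording is ambiguous and worth clarifying, no more.

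**Conclusion.** The analysis rule is wrong as written: right-censored arms enter an ordinary mean, SD and 95% limit as observed failures at 12 h. The output is an unlabelled mean restricted to 12 h. When many arms last to the cap, its SD understates the spread and its interval is unreliable.

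The size depends on the true PT: nothing of consequence at 8 to 10 h, and material from about 12 h upward for either target. These figures rest on assumed normality and an SD of 2 h carried over from an 8 h PT. The result for all arms surviving rests on neither assumption.

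**What to change.** In the Data Analysis section, replace the rule of assigning twelve with a statement that arms without FCB at 12 h are right-censored at 12 h. For each product and each site, report:

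- the Kaplan-Meier curve;
- the median PT with 95% CI, given as not reached where that applies;
- the proportion of arms protected at 12 h with an exact 95% CI.

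If a mean is kept, either label it as restricted to 12 h or take it from a censored parametric model. The label alone does not repair the t interval, so the exact proportion should stand beside it.

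Also clarify that test termination means FCB or 12 h, and that arms unbroken at an earlier cancellation are censored at the last completed exposure and not given twelve. State how this fits with the existing exclusion of dropouts, since a general censoring rule would otherwise appear to bring them back in.

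The cost is rewording and survival-analysis software, with no extra subjects, exposures or procedures. The downside is that the median may be reported as not reached instead of as one number, and a censored parametric mean has no finite estimate if every arm lasts.
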